## Hypotheses

There are two goals of the proposed preliminary work. The first is to determine whether there are metabolic differences in the brain stem in healthy individuals as a result of peripheral administration of BOTOX into the glabellar muscles. This is an open question that can be addressed with MRS. While the doses used in cosmetic treatments are low, an effect via the trigeminal nerve is certainly possible and knowing whether such an effect exists in this cohort would be highly relevant for attempts to understand the effects of BOTOX on disorders such as migraine or depression. Importantly, we proposed to diverge from typical MRS here and to employ “functional MRS” by collecting MRS data during the performance of an emotionally-arousing task. If BOTOX is altering emotional processing in the brain via a “facial feedback” mechanism, altered metabolite levels in the brainstem might be resolved.

The second goal is to better understand the effect of BOTOX on functional activity (measured using fMRI) in the brain and in the brainstem. Consistent with prior work, we propose that BOTOX will alter emotional-related activity in the amygdala (Kim J, 2014). We propose to extend this work in several ways by measuring fMRI activity in the brainstem as well and understanding its relationship to activity in structures such as the amygdala. Again, if BOTOX is altering emotional processing via an alteration of the facial feedback mechanism, this could be resolved either as an alteration of fMRI activity levels or as an alteration in “functional connectivity” (correlation of activity over time) between the brainstem and the amygdala.

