## Proposed Protocol: Pilot Study on Healthy Controls

Our aim is to be able to examine the effects of BOTOX on the CNS to determine potential mechanisms for the effects of BOTOX on disorders such as migraine and depression. To date, there are no MRS studies of BOTOX to guide the investigation. We therefore propose a staged design with an initial pilot study in healthy controls undergoing BOTOX treatment for cosmetic purposes, potentially followed by an expanded study in patients being treated for migraine or depression. Additionally, in this initial pilot, we will explore the feasibility of brainstem fMRI in those two groups of participants. The connectivity between regions in the brainstem will be studied in the presence of angry/happy faces paradigm and at rest. Possible connections with metabolite changes will be explored as well.

**Participants:** We propose to scan 10 healthy, right handed females. Because the sample size is so small, we will be constraining the inclusion/exclusion criteria to minimize variability. Participants will be naïve BOTOX users (e.g. no previous use of BOTOX), ages 30-40 years old. Participants will be excluded for the presence of neurological or psychiatric conditions or the presence of any risk factors for MRI. Participants will be recruited from UCI and/or the surrounding community via e-mail blasts and word-of-mouth. They will receive \$50 compensation per MRI scan and the cosmetic BOTOX will be provided by Allergan.

**Design:** We propose a pre- and post-design. One scan will be collected prior to BOTOX injection and the second will be collected 2-4 weeks post-injection. BOTOX injections will be limited to 20 units in the glabellar area, as approved by the FDA and administered by a

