## Measuring the effects of BOTOX on the brainstem using MR Spectroscopy (MRS) and fMRI

certified clinician at the UC Irvine Medical Center (ENT Satellite Office in Irvine). Each scanning session will last approximately one hour and include:

- 1) T1 MPRAGE (3D whole-brain structural image) = 5 min
- 2) T2 localizers (axial, coronal and sagittal) = 6 minutes
- 3) Resting state fMRI = 7 minutes
- 4) fMRI (reduced TR and FOV) = 15 min
- 5) MRS–SV of brain stem = 7 min

**MPRAGE:** This is a standard 3D structural image of the whole brain that will allow us to localize all fMRI findings as well as to determine whether there are any pre-existing cortical abnormalities in any participants. While we do not expect to observe any pre- vs. post-structural changes regional brain shape or size, we will be able to assess these factors.

**Resting-state fMRI:** We will collect whole-brain fMRI data for 7 min of eyes-open resting state fMRI. This data is commonly used to reveal patterns of network-level connectivity (and group-level changes in connectivity) in the brain (Power et al., 2011). Changes in resting states between groups (with and without BOTOX) would likely be observed. We will examine the frequency of switching of modes (unique waveforms from multi-component analysis) between groups. We will also explore the functional connectivity between dura-sensitive neurons and their projections to the hypothalamus, thalamus and mid-brain, as shown by Burstein (Burstein et al., 1998).

**fMRI:** The volunteers will participate in an fMRI scanning session following the protocol of Kim et al. 2014. Photos of series of angry, happy and surprised facial expressions (consisting of 9 male and 9 female identities) will be presented for 17, 50 and 1000 ms followed by black and white pattern, presented for 250 ms (serving as a retinal wipe). During each trial, participants will be asked to report using a button box whether they thought each of the faces they saw represent a positive or a negative emotion. We will analyze fMRI data of the brainstem following a modified method used by Beissner et al. 2011.

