1

Measuring the functional effects of BOTOX on the brainstem using MR Spectroscopy (MRS) and fMRI

PI: [name]., Professor

[name] Department of Neurobiology & Behavior University of California, Irvine [name] [contact] [contact]

STATISTICAL ANALYSIS PLAN

MRS Data Analyses

Metabolite FIDs will be averaged within each task and processed using TARQUIN (v.4.3.6) software for spectral fitting. We chose a block design (vs. event-related) for its higher detection efficiency (at the cost of the inability to sort by individual trial performance or estimate HRF shape)⁷⁵. Within-task dynamics will be investigated by a moving average windowing approach. The minimum temporal window will be determined by the SNR. The corresponding binned water unsuppressed spectra will be used as an internal reference for each condition. The acquired MRS spectra will be corrected for tissue type and T2 relaxation differences. Additionally, using TARQUIN we will obtain values for all metabolites mentioned in Preliminary results. These values will be collected to ensure that the changes in Glu and GABA signals are real and not due to a result of some other general effect on the MRS data (e.g., BOLD related change in signal). The water peak amplitude changes will be processed with a custom designed MATLAB script⁵.

Functional MRI Data Analyses

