The **functional MRI data** will be pre-processed and analyzed using AFNI (Cox, 1996; afni.nimh.nih.gov) and in-house programs written in Matlab and Python. The fMRI data were first subjected to a traditional general linear model analysis using multiple regression in AFNI (Cox, 1996). The task vectors of interest will be individually modelled for each participant's functional data utilizing a deconvolution approach built into AFNI's 3dDeconvolve (Ward, 2001). 15 tent functions will be used to estimate the hemodynamic response to each condition. The resultant fit coefficients (β coefficients) represent activity versus baseline for each condition of interest at a given time point in each voxel. The sum of the resultant fit coefficients over the bulk of the expected hemodynamic response (3-13.5 seconds after trial onset) will be taken as the model's estimate of the response for each trial type and passed on to group-level analyses. The hypotheses will be primarily tested using the standard linear model. Brain activity for positive and negative emotions pre- and post-BOTOX injection will be compared in a 2x2 ANOVA, with planned comparisons for follow-up.

Resting state data will be detrended using 2nd order Legendre polynomials. The time series will be normalized to have zero mean and unit variance and the motion vectors and first derivatives will be regressed out of the signal. The first 6 principal components of the variance will be computed using CompCor (not including global signal) and regressed out of the signal (Behzadi et al., 2007). The data were then temporally bandpass filtered (0.009 to 0.08 Hz) and TRs with framewise displacement >0.5mm, as well as those one TR before and two TRs after, will be removed.

Structural brain volumes will be calculated on the MP-RAGE for each participant using Freesurfer's automatic software for volumetric measures (FreeSurfer 2016; Fischl et al. 2002). These volumes will then be normalized by dividing by total intracranial volume for each participant. T-tests for pre- vs. post- BOTOX injections can then be examined.

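### Does the positive/negative 2x2 ANOVA need a stated rule for the surprised faces before it can be run as planned?

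*SAP*

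**What the plan says.** The fMRI paragraph of the protocol's Proposed Protocol section describes the task: "angry, happy and surprised facial expressions (consisting of 9 male and 9 female identities) will be presented for 17, 50 and 1000 ms". For every face, participants are "asked to report using a button box whether they thought each of the faces they saw represent a positive or a negative emotion". Earlier in the same section, the task is given a shorter label in a sentence on brainstem connectivity, which "will be studied in the presence of angry/happy faces paradigm and at rest".

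The SAP, under Functional MRI Data Analyses, works in two stages. At the participant level, "15 tent functions will be used to estimate the hemodynamic response to each condition", and the fitted coefficients "represent activity versus baseline for each condition of interest at a given time point in each voxel". Each trial type's summed response then goes to the group level, where the one task-fMRI test is: "Brain activity for positive and negative emotions pre- and post-BOTOX injection will be compared in a 2x2 ANOVA, with planned comparisons for follow-up".

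Under MRS Data Analyses, the SAP says that a block design was chosen "at the cost of the inability to sort by individual trial performance or estimate HRF shape".

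The Hypotheses section of the protocol sets the aim: "we propose that BOTOX will alter emotional-related activity in the amygdala".

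No sentence in either document says whether surprised faces are counted as positive, counted as negative, sorted by the participant's answer, or left out.

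**The concern.** Three expressions in two sessions make six expression-by-session cells. The ANOVA has four, and the map from six to four is not written down. Angry and happy have obvious places; surprise does not. The protocol's short label points towards leaving it out. The forced positive-or-negative answer could point towards counting it. The remark on trial sorting would rule out allocation by response, but it sits in the MRS section. Its clause on the shape of the haemodynamic response also does not fit the tent-function model, so its reach to this task is unclear.

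At stake is what the emotion-by-session interaction estimates. If surprise is averaged into a cell whose expression it does not resemble, the angry-minus-happy contrast shrinks, even if that coding was fixed beforehand. If the coding were picked after seeing the results, the false-positive rate would rise as well. This is the only group test of the task data, so the gap deserves a check.

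**Working it through.** The documents give no effect size, standard deviation, power or significance level, so there is no plan figure to reproduce. The only input from the documents is n = 10, in one group scanned before and after injection (protocol, Proposed Protocol section). Everything else here is assumed for illustration.

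**Contrasts.** Let A, H and S be the post-minus-pre change for angry, happy and surprised faces. With equal numbers of trials per expression (assumed), the interaction is:

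- surprise left out: A − H
- surprise counted negative: (A + S)/2 − H
- surprise counted positive: A − (H + S)/2

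These are three different estimands. If only surprise changed (A = H = 0, S = −1), they would be 0, −0.5 and +0.5, so even the sign would depend on the coding.

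**Power, equal variances and equal pairwise correlation ρ.** Var(A − H) = 2σ²(1 − ρ) and Var((A + S)/2 − H) = 1.5σ²(1 − ρ). Let d be the standardised effect of A − H, and let f place surprise between happy (0) and angry (1). Counting surprise as negative gives d × (1 + f)/2 × √(2/1.5). Counting it as positive is the mirror image. With d = 1.0, a paired t-test on 9 df and two-sided 5%:

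| Coding | Standardised effect | Power |
|---|---|---|
| Left out | 1.000 | 80% |
| Counted with the expression it resembles | 1.155 | 90% |
| Midway, either cell | 0.866 | 68% |
| Counted with the other expression | 0.577 | 37% |

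**How firm is the 37%?**

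- *Unequal correlation.* Take f = 0 (surprise behaves like happy), surprise counted negative, surprise–happy correlation r and the other correlations 0.3. Then Var(A − H) = 1.4σ², Var((A + S)/2 − H) = (1.35 − r)σ², and the standardised effect is 0.5 × √(1.4/(1.35 − r)). For r = 0.3, 0.6 and 0.9 this is 0.577, 0.683 and 0.882, with power 37%, 49% and 70%. If S equals H exactly, the contrast is (A − H)/2, which has the same standardised effect as A − H, and no power is lost.
- *Share of the cell.* If surprise is one third of the cell, correlations equal, the effect is (2/3) × √(2/(14/9)) = 0.756 and power is 57%.
- *Fixed contrast SD.* If averaging brings no gain in precision, the effects for other cell, midway and matching cell are 0.50, 0.75 and 1.00, with power 29%, 56% and 80%.

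**Choosing the coding afterwards.** Taking the most favourable of the three codings would raise the interaction's false-positive rate from 5% to about 10% (simulated). Nothing in the documents suggests that such a choice is planned.

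**Reading the text.** The connectivity sentence uses a label; it does not say that surprised faces are absent. The fMRI paragraph is the operational description and says that they are shown. The SAP fits each condition separately before comparing positive with negative. All three fit together if angry is negative, happy is positive, and surprise is modelled as its own condition without entering the 2x2. Under that reading the interaction is A − H, and its power does not depend on how surprise behaves.

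**The case for a change.** The strongest case for a change is that two competent analysts could run different tests from this SAP. Surprise has no default valence, participants must call it positive or negative, and a poor allocation costs power without any misconduct. The remedy would be one paragraph and no new data.

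Part of this stands. The allocation is not written down, and the three codings do estimate different things. The rest is weaker. The large loss arises only if an analyst counts surprise and puts it in the wrong cell, which no text instructs. The size of the loss moves widely with assumptions that the documents cannot settle. Leaving surprise out is itself a trade-off: in the equal-correlation case it gives up 10 points of power (80% against 90%) if surprise would have been placed correctly. The written rule one would ask for is the same as the natural reading, so the analysis would not alter. The fMRI paragraph also says that the session follows a published protocol, which may settle the handling of expressions; that source was not available here and the conclusion does not lean on it.

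**Conclusion.** The gap is real but small, and no change to the plan follows. The protocol's two descriptions of the task differ loosely in wording and do not contradict each other. The SAP leaves the place of surprised faces unspecified; it does not give them a wrong one. The natural reading gives a sound within-participant test, with 80% power in the illustration. The loss to about 29% to 70% needs a coding that the text does not call for. It also rests on n = 10, an assumed two-sided 5% level, an assumed standardised effect of 1.0, and the stated variance, correlation and trial-share assumptions. In an exploratory pilot with no stated significance level, this is detail that an analyst can settle sensibly and report with the results.

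### Resting-state data are band-pass filtered before high-motion TRs are removed, so motion artefact spreads into the retained TRs and can bias connectivity in either direction

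*SAP*

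**What the plan says.** The SAP, under Functional MRI Data Analyses, lists the resting-state steps in sequence: detrending, normalisation, then nuisance regression, in which "the motion vectors and first derivatives will be regressed out of the signal". Next comes CompCor: "The first 6 principal components of the variance will be computed using CompCor (not including global signal) and regressed out of the signal". The last sentence reads "The data were then temporally bandpass filtered (0.009 to 0.08 Hz) and TRs with framewise displacement >0.5mm", and continues "as well as those one TR before and two TRs after, will be removed". Neither document describes interpolating, replacing or down-weighting flagged TRs before the regressions or the filter.

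The protocol says how these data will be used. In Proposed Protocol: Pilot Study on Healthy Controls: "The connectivity between regions in the brainstem will be studied in the presence of angry/happy faces paradigm and at rest". In the Resting-state fMRI paragraph: "Changes in resting states between groups (with and without BOTOX) would likely be observed". The design is single-arm: "We propose a pre- and post-design", with 10 participants. The resting-state TR is not stated. The TR of 2 in the Figure 3 caption belongs to the pilot high-resolution image.

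**The concern.** Removing a flagged TR with one before and two after is meant to delete motion-contaminated data. It can do so only if the contamination lies inside those four TRs. A narrow low-frequency band-pass filter turns a one-TR spike into a wave lasting many seconds, so if the filter runs first, part of the artefact falls in TRs that are kept. Because high-motion TRs also enter the motion and CompCor fits, they can distort those coefficients as well.

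What remains can move a correlation between two regions up (spikes of the same sign in both), down (opposite signs) or toward zero (random relative signs). If participants move more at one scan than the other, the mean pre/post change shifts, and a single-arm design cannot separate that shift from a BOTOX effect. Brainstem connectivity at rest is planned explicitly. Relevance to brainstem–amygdala connectivity at rest is an inference, because the Hypotheses section names that pair without saying at rest.

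**Working it through.** **Inputs.** Band 0.009–0.08 Hz and a four-TR removal window (SAP). Run length 7 min = 420 s and n = 10 (protocol). Assumed: TR 2 s (range 1–3 s); filter type (ideal FFT or zero-phase second-order Butterworth); 5–10 spikes per run of 2–5 SD; lag-1 autocorrelation 0.4. The plan gives no figure of its own to reproduce.

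**Step 1: width of the filtered spike.** The ideal band-pass response is proportional to [sin(2π·0.08·t) − sin(2π·0.009·t)]/t. It first reaches zero at t = 1/[2 × (0.08 + 0.009)] = 5.6 s. At TR 2 s the removed TRs span −2 s to +4 s, which is shorter than the main lobe on both sides.

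**Step 2: energy left behind, TR 2 s, FFT filter.** There are 420/2 = 210 TRs. The passband holds 30 frequencies (4/420 to 33/420 Hz), so the filtered peak is 60/210 = 0.2857, and the total filtered energy is also 0.2857. Filtered values are 0.2350 at ±1 TR and 0.1113 at ±2 TRs. Energy inside the window (−1 to +2) is 2 × 0.2350² + 0.2857² + 0.1113² = 0.1105 + 0.0816 + 0.0124 = 0.2045. The share outside is 1 − 0.2045/0.2857 = 0.284. The retained TR just before the window carries 0.1113/0.2857 = 39% of the peak (27% with Butterworth). Before filtering, the share outside is zero.

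| TR (s) | Outside, FFT | Outside, Butterworth |
|---|---|---|
| 1 | 0.501 | 0.353 |
| 1.5 | 0.357 | 0.222 |
| 2 | 0.284 | 0.170 |
| 3 | 0.235 | 0.145 |

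These shares do not depend on how many spikes there are or how large.

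**Step 3: effect on a correlation.** Simulated pairs of series, TR 2 s, true r = 0, same-sign spikes, SAP order, 3000 runs per cell. Mean r:

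| Spikes | Size (SD) | FFT | Butterworth |
|---|---|---|---|
| 5 | 2 | 0.014 | 0.009 |
| 5 | 3 | 0.032 | 0.019 |
| 5 | 5 | 0.088 | 0.050 |
| 10 | 2 | 0.030 | 0.014 |
| 10 | 3 | 0.069 | 0.029 |
| 10 | 5 | 0.162 | 0.084 |

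- Opposite signs mirror these values: −0.163 (FFT) and −0.085 (Butterworth) in the last row.
- Random relative signs give about 0 at true r = 0. At true r = 0.4, 10 spikes of 5 SD lower r to 0.328 (FFT) or 0.361 (Butterworth).
- Adding 12 motion and 6 CompCor-like regressors leaves shifts of 0.012 to 0.148 in either direction (FFT).

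**Step 4: pre/post contrast.** n = 10, no true change, paired t-test on Fisher z. With a between-run SD of r of 0.13–0.15, the SE of the mean change is √2 × 0.13/√10 = 0.058 to √2 × 0.15/√10 = 0.067. For 5 spikes at one scan and 10 at the other, same sign:

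| Size (SD) | Shift, FFT | False positives | Shift, Butterworth | False positives |
|---|---|---|---|---|
| 2 | 0.016 | 4.2% | 0.008 | 3.8% |
| 3 | 0.030 | 6.1% | 0.020 | 6.3% |
| 5 | 0.075 | 19.6% | 0.044 | 8.5% |

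The highest rate for 5 versus 10 spikes was 21.8% (FFT, opposite sign, 5 SD). In a deliberately extreme case, 0 versus 10 spikes of 5 SD, the shift is 0.16 (FFT) or 0.09 (Butterworth), with false positives of about 70% or 22–25%. With equal motion at both scans the bias cancels, and the rate is 4–6%.

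**The case against.** The strongest reply is that the order is inferred. The closing sentence mixes tenses and joins filtering and removal with a plain conjunction, so it may not be meant as a strict sequence. That is fair, but no text supports another order, and an analyst following the SAP would filter first. If another order is intended, the wording still needs correcting.

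Second, nothing in the documents shows how much participants will move. The shifts in r rest on assumed spikes that survive nuisance regression and share one sign relation. At 2–3 SD, 5 versus 10 spikes leaves the false-positive rate close to nominal. This stands: material bias is possible but not demonstrated.

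Third, the size depends on the signal model. For 10 same-sign spikes of 5 SD (FFT), a band-limited signal with added white noise gives a mean r of 0.103 instead of 0.162. Setting the autocorrelation to 0 gives 0.23–0.25, and 0.6–0.8 gives 0.13–0.14. The direction holds throughout, but 0.16 is not an upper bound.

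Fourth, the SAP names no connectivity statistic, test or alpha for the resting-state data, so the false-positive rates illustrate a plausible test and are not the plan's own error rates. The planned mode-switching analysis was not examined.

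Finally, this is a 10-person pilot that already has motion regression, CompCor and censoring. That limits the consequence but does not make the order sound.

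**Conclusion.** The concern holds, and the order should be changed. As written, censoring does not remove what it is meant to remove: about 15–50% of filtered spike energy stays in the retained TRs over TRs of 1–3 s. That part follows from the SAP's own band and window, given the run length, TR and filter type. The resulting bias in connectivity runs from negligible (about 0.01) to substantial (about 0.16 under the main assumptions) and can go either way. It reaches the pre/post contrast only as far as motion differs between scans. The finding is confined to the resting-state analysis; the task 2x2 ANOVA, the MRS analysis and the volumetric comparisons are not affected. Confidence is medium, because the order is a plain reading of ambiguous wording and the amount of motion is unknown.

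**What to change.** State the processing order, the filter type and the resting-state TR in the SAP, before any data are analysed:

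1. Flag high-motion TRs and their neighbours first.
2. Leave flagged TRs out of the nuisance-regression fits.
3. Interpolate across them.
4. Band-pass filter.
5. Drop the flagged TRs from the connectivity estimates.
6. Report framewise displacement and the number of retained TRs for each scan, so that a pre/post motion difference is visible.

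Deleting TRs and then filtering the gapped series is not a substitute.

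The cost is wording and one processing step. In simulation, interpolating before the filter kept mean r within 0.004 of its spike-free value, kept the mean pre/post change within 0.003 of zero, and gave false-positive rates of 4–6%. The between-run SD of r rose by at most 0.014 at TR 2 s (0.128 to 0.142) and 0.022 at TR 3 s (0.133 to 0.155).

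A single joint regression with a censor list is an option only for low-motion runs. With 10 spikes at TR 2 s, 30 × 2 = 60 passband dimensions less 18 regressors and about 38 censored TRs leaves about 4 degrees of freedom. The SD of r was then 0.62–0.65 (0.21–0.23 with 5 spikes), against 0.14–0.17 for the SAP order.
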